3.3.5.1 CPRD Manual Patient Profile Review

Indication will be further assessed in random samples of users through the manual review of computerised patient profiles created from the CPRD database. The patient profile is a de-identified chronological list of medical events and drug prescriptions based on the computerised database information, including free-text information if available. Review of these profiles will provide insight into medical events leading up to the prescription of a new course of medication. This information will also be used to validate the created computer algorithms to identify clinical indications. The target number will be at least 200 patient profiles. However, this number might be increased for the validation exercise if the number of sub-groups by potential clinical indication is larger than eight, to allow for a minimum review of 25 patient profiles per sub-group. Additional samples will be reviewed if the created computer algorithms need to be modified.

3.3.6 Study size

The study size will be driven primarily by the uptake of dabigatran etexilate in the populations from which the automated databases obtain data. The estimated study size for each country-specific database is approximately 5,000 new users of dabigatran etexilate. As can be seen in [Table 2](#), a study size between 2,000 and 5,000 patients per database offers an

acceptable level of precision in the different scenarios of available number of users. However, with 5,000 patients, at the 95% level of confidence the level of precision could be adequate even when estimating the percentage of off-label use by different groups of clinical use. The final study size will depend of the uptake of the medication in each country.

Table 2 Binomial confidence intervals for different study sizes and possible percentages of off-label use

Number of patients	Lower and upper bounds of 95% confidence intervals for example off-label use percentages (%)									
	1%		2%		5%		7%		10%	
2000	0.6	1.5	1.4	2.7	4.1	6.0	5.9	8.2	8.7	11.4
3000	0.7	1.4	1.5	2.6	4.2	5.8	6.1	8.0	8.9	11.1
4000	0.7	1.4	1.6	2.5	4.3	5.7	6.2	7.8	9.1	11.0
5000	0.7	1.3	1.6	2.4	4.4	5.6	6.3	7.7	9.2	10.9

Note: Calculations were performed using Stata software.

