The Cegedim panel of participating medical doctors is selected from a large number of French physicians who use the Cegedim management software for their daily practice. These office-based, active physicians have agreed to upload to CSD servers anonymous and coded excerpts from medical files of patients who have come to see them. The data collected are gathered for each patient within the same doctor's office, thus providing longitudinal data on the same patients. The representativeness of the panel of physicians is checked using three criteria known to influence prescribing: age, sex, and geographic area of coverage. However, there are limitations in this database such as no availability of information on hospitalisations, deaths, or date transferred out of the system. Data from panels of primary care physicians and data from specialist panels are available. Panels of specialists are independent of GP panels; therefore, an overlap between patients included in primary health practices and in those from specialists could occur but it is not possible to link individual patients across the two types of practitioners. For this study, it is planned to include also information gathered by cardiologists due to the potential that the first prescription of Pradaxa will be issued by these specialists. Therefore, all the information should be stratified by the type of panel and clinical specialty. Oral anticoagulants are expected to be recorded completely when prescribed by the physicians participating in the panel; however, the first prescription can be missed if issued in the hospital or outside of the participating physicians.

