3.7.1 Main analysis by indication

The main analysis will be to estimate (with 95% confidence intervals) the prevalence proportion of off-label use among new users of dabigatran etexilate during the overall study period in each of the study populations. This will include potential off-label clinical indications and contraindications. The proportion of each of the most common off-label use indications will be described among the overall off-label use group. The proportion of identified users in the pediatric age subgroup will be described.

In addition, separately for each approved clinical indication, the risk profile and use of selected drugs among new users of dabigatran etexilate will be described.

The distribution of the dispensed formulation strength or the daily prescribed dose at the index date based on the index prescription will be described, overall and by on-label and off-label indication sub-group. The proportion of new users within the primary VTE prevention subgroup with one or more follow-up prescriptions after the recommended treatment duration will be described. The follow-up prescriptions will be assessed in the 90-day time window after the index prescription.

To evaluate the differences between sub-groups by indication, proportions for categorical variables and means for continuous variables will be estimated (with 95% confidence intervals) within each sub-group. If appropriate, medians will be used instead of means when the variables of interest do not assume a normal distribution.

All the results will be presented for each country-specific database. In addition, for France, all the data will be stratified by type of physician panel: primary care or cardiologist. As part of the analysis, tables presenting the results will be generated. Table shells for the key descriptive analyses will be developed for the detailed, database-specific protocol.

A weighted, pooled prevalence of off-label use among new users of dabigatran etexilate for the entire study population (CPRD, Cegedim, and Danish national databases) will be estimated (with 95% confidence intervals) when the individual results of all three databases are available.

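### Table 2 assumes independent users, so its precision is a best case for CPRD and Cegedim, where users are sampled through practices and physicians

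*Protocol*

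**What the plan says.** Protocol section 3.3.6 sets the target: "The estimated study size for each country-specific database is approximately 5,000 new users of dabigatran etexilate". Precision is shown in Table 2, headed "Binomial confidence intervals for different study sizes and possible percentages of off-label use", whose columns give "Lower and upper bounds of 95% confidence intervals for example off-label use percentages". From this table the section concludes that 2,000 to 5,000 users in a database are acceptable for precision, and that "with 5,000 patients, at the 95% level of confidence the level of precision could be adequate", including where off-label use is split by group of clinical use. It mentions no design effect.

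The sampling is described elsewhere. Section 3.3.4 restricts CPRD to permanently registered patients of participating practices that meet the database's quality standard. For France, section 3.1.2 says "The Cegedim panel of participating medical doctors is selected from a large number of French physicians", with data gathered within each doctor's office. On the primary care and specialist panels it adds: "an overlap between patients included in primary health practices and in those from specialists could occur but it is not possible to link individual patients". It therefore asks for stratification by panel and specialty.

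Section 3.7.1 makes the main analysis "the prevalence proportion of off-label use among new users of dabigatran etexilate during the overall study period in each of the study populations", with 95% confidence intervals. It stratifies France by panel and plans a weighted pooled prevalence over the three databases. It names no interval method. The limitations in section 4 mention neither clustering nor patients who appear in both French panels.

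**The concern.** A binomial limit at n patients is right only if users are independent. Here the outcome is whether a prescription falls outside the label, classified from diagnoses that the prescriber recorded or from proxies built on recorded codes. Both prescribing habits and coding habits belong to the practice or physician. Section 3.1.2 itself checks the French panel on physician characteristics that it says influence prescribing. Two users from one practice are therefore likely to be more alike than two users from different practices, and 5,000 such users carry less information than 5,000 independent ones.

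The overlap in France works in the same direction. Cardiologists are included because they may write the first prescription (section 3.1.2), while most follow-up prescriptions are expected from GPs or primary care physicians (section 3.1). The index prescription is the first one captured (section 3.3.2). A patient started by a panel cardiologist and continued by a panel GP could therefore qualify as a new user in each panel. At stake is the protocol's statement of how precisely off-label use will be known in two of the three countries and in the pooled figure.

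**Working it through.** **Step 1: reproduce Table 2.** Inputs are n = 2,000, 3,000, 4,000 and 5,000, and p = 1, 2, 5, 7 and 10%, all from Table 2. With x = p × n, the exact (Clopper-Pearson) limits are the 0.025 quantile of Beta(x, n − x + 1) and the 0.975 quantile of Beta(x + 1, n − x). For n = 5,000 and p = 5%, x = 250, and the limits are 4.41% and 5.64%, against the stated 4.4 and 5.6. Rounded to 0.1 point, the exact limits match 40 of 40 bounds (Wald 28, Wilson 32). The arithmetic of Table 2 is correct, and there is no room in it for a design effect.

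**Step 2: allow for clustering.** The documents give no ICC, no number of practices or physicians, and no users per practice. Assumed here: m = 5 to 20 users per practice or physician, and ICC = 0.02 to 0.10.

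- Design effect: DE = 1 + (m − 1) × ICC
- Lowest: 1 + 4 × 0.02 = 1.08
- Highest: 1 + 19 × 0.10 = 2.9
- Effective size: n / DE, followed by the exact limits at that size

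Results at 5% off-label use:

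| m, ICC | DE | Effective size, n = 5,000 | 95% limits | Effective size, n = 2,000 | 95% limits |
|---|---|---|---|---|---|
| Table 2 (independent) | 1 | 5,000 | 4.4–5.6 | 2,000 | 4.1–6.0 |
| 5, 0.02 | 1.08 | 4,630 | 4.4–5.7 | 1,852 | 4.1–6.1 |
| 10, 0.02 | 1.18 | 4,237 | 4.4–5.7 | 1,695 | 4.0–6.1 |
| 10, 0.05 | 1.45 | 3,448 | 4.3–5.8 | 1,379 | 3.9–6.3 |
| 20, 0.05 | 1.95 | 2,564 | 4.2–5.9 | 1,026 | 3.7–6.5 |
| 20, 0.10 | 2.9 | 1,724 | 4.0–6.1 | 690 | 3.5–6.9 |

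**Step 3: compare with the protocol's own standard.** The smallest size that section 3.3.6 calls acceptable is 2,000. Since 5,000 / 2.5 = 2,000, the full target falls below that row only if DE exceeds 2.5. A database with 2,000 users falls below it at any DE above 1. The footnote to Table 6 allows a start with fewer than 5,000 users where uptake is slow, so the lower end of the range could be reached.

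**Step 4: French overlap.** The documents give no rate. As an illustration only, suppose that a share d of 5,000 combined French records are second copies with the same classification. The variance is then multiplied by 1 + 2d. For d = 5, 10 and 20% this is 1.1, 1.2 and 1.4, with effective sizes of 4,545, 4,167 and 3,571. Within a single panel this cross-panel duplication does not arise.

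**The case against.** Four points on the other side carry weight.

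- **Analysis intervals.** A reader might infer that the confidence intervals for the main outcome will be too narrow. The protocol does not support this: section 3.7.1 names no method, and a clustered variance could still be set in the analysis plan or the database-specific protocols. Only Table 2 and the precision claim resting on it are fixed here.
- **Size.** A reader might also infer that the claimed precision will not be delivered. That cannot be shown, because every clustering input is assumed. At a DE of 1.18 the 5,000-user interval moves by about 0.1 point, and the 2.9 needs both extremes together. Even then, 4.0–6.1 is close to the 2,000-user row of 4.1–6.0.
- **Consequences.** The study is descriptive and tests no hypothesis, and its size is driven mainly by uptake. Restating Table 2 would not change who is included.
- **France.** The overlap is disclosed, and stratification by panel deals with it inside each panel. It can affect only a combined French count and the pooled estimate. It may seem natural to take the French figure from primary care alone. However, sections 3.1.2 and 4 say that specialists may write many first prescriptions, so this would exchange an unquantified duplication for a possible selection bias.

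What stands against these points is narrow. The study-size justification is fixed in this document, its independence assumption is not stated, and the described sampling of two databases does not fit it.

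**Conclusion.** The point holds as a limit on what Table 2 can support. Its numbers are correct for independent users and are a best case for CPRD and Cegedim. The direction follows from any positive correlation within practice or physician, which is likely for this outcome but is not documented. The size rests on the assumed 5 to 20 users per cluster and ICC of 0.02 to 0.10, and on a formula that takes clusters to be of equal size. On those assumptions the total width at 5% off-label use and 5,000 users grows from about 1.2 points to between 1.3 and 2.1. The conclusion that 5,000 users give acceptable overall precision survives most of this range; the same conclusion at 2,000 users has no margin. The point is not made for Denmark, where the national registries cover all residents. The effect of overlap between the French panels on the combined and pooled figures is real in principle and of unknown size.

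**What to change.** 1. In section 3.3.6, state that Table 2 assumes independent users, and add rows for design effects of about 1.2, 1.5 and 3. At 5% and 5,000 users these rows read 4.4–5.7, 4.3–5.8 and 4.0–6.2.
2. State that the 95% intervals for CPRD and Cegedim, and their contribution to the pooled interval, use variance clustered by practice or physician.
3. For France, keep the panel-stratified results as primary. Show the pooled estimate with and without the cardiologist panel as a sensitivity analysis, and do not drop that panel. Add the possible overlap to the limitations in section 4.

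The cost is a longer table, a few sentences, a variance option in the analysis program and one extra pooled estimate. The reported intervals will be somewhat wider. No data collection or inclusion rule changes.

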3.4 EXPOSURES

The exposure of interest is dabigatran etexilate.

3.4.1 Dose

The distribution of the daily prescribed dose at the index date will be described for all new users of dabigatran etexilate as well as by indication sub-group (on- or off-label use). The dose described will be the one associated to the index prescription. The daily dose of medications is recorded in the CPRD (UK) and Cegedim (France). The capsule strength will be used to estimate dose in the Danish national databases. However, the degree of completeness is variable across databases. Imputations for missing values or other methods to describe daily dose will be evaluated (i.e., calculation of defined daily doses).

3.5 OUTCOME(S)

The main outcome of this study is the proportion of off-label use estimated among new users of dabigatran etexilate and their characterisation.

3.5.1 On-label use definition

On-label use is when a medication is used as described in the approved drug label. As of 1 August 2011, the EMA-approved indications for Pradaxa were as follows:

- Primary prevention of venous thromboembolic events in adult patients who have undergone elective total hip replacement surgery or total knee replacement surgery.
- Prevention of stroke and systemic embolism in adult patients with non-valvular atrial fibrillation with one or more of the following risk factors:
 - Previous stroke, transient ischaemic attack, or systemic embolism (SEE)

- Left ventricular ejection fraction < 40%
- Symptomatic heart failure, New York Heart Association (NYHA) Class 2 or higher
- Age \geq 75 years
- Age \geq 65 years associated with one of the following: diabetes mellitus, coronary artery disease, or hypertension

A revision of this indication statement was submitted for approval in the EU in September 2013. The revision became effective in December 2013, introducing the following modified indication statement: “Prevention of stroke and systemic embolism in adult patients with non-valvular atrial fibrillation (NVAF) with one or more risk factors, such as prior stroke or transient ischemic attack (TIA); age \geq 75 years; heart failure (NYHA Class \geq II); diabetes mellitus; hypertension.”

The indication application for treatment or secondary prevention of venous thromboembolism EMA/H/C/00829/II/48G obtained a positive CHMP opinion on 25 April 2014 with the following indication statement: “Treatment of deep vein thrombosis (DVT) and pulmonary embolism (PE), and prevention of recurrent DVT and PE in adults.” During the study period, use associated with these indications will be considered off-label use until Commission Decision. The definition of on-label use will have to consider regulatory label changes that have occurred during the product life cycle with respect to indication and also to contraindications (e.g., addition of dronedarone use to the list of contraindications since 30 August 2012). Therefore on-label use will be defined considering the index date and the appropriate label indication and contraindication applicable during the time period comprising the index date.

[Table 3](#) and [Table 4](#) display the preliminary lists of diseases, conditions, and procedures mapped to the ICD-10-CM codes for identification of the current approved indications. ICD-10-CM codes are used in the Danish national databases and in Cegedim (France); Read codes and ICD-10-CM codes are used in the CPRD (UK). These lists of codes will be used to identify the group of on-label users of dabigatran etexilate in each population. The complete list of codes will be available in the detailed, database-specific study protocol.

Two levels of on-label use will be investigated:

- The first level will include a broad definition based on the main code(s) for the approved clinical indications, e.g., atrial fibrillation.
- The second level will include a more restrictive definition by excluding patients with conditions for which the medication might not be indicated within the broad definition, e.g., valvular heart disease or low-risk patients with non-valvular atrial fibrillation.

Table 3 Preliminary list of diagnoses and corresponding ICD-10-CM codes for identification of new users of dabigatran etexilate for primary prevention of venous thromboembolism following total hip or knee replacement surgery

Disease/condition or procedure	ICD-10-CM description	ICD-10-CM code	Use of codes in indication definitions
Total hip replacement	Presence of artificial hip joint	Z96.64*	Primary code for the broad definition of the clinical indication
Total knee replacement	Presence of artificial knee joint	Z96.65*	Primary code for the broad definition of the clinical indication
Absence of venous thromboembolism between total hip or knee replacement surgery and dabigatran etexilate initiation **	Phlebitis and thrombophlebitis of femoral vein Phlebitis and thrombophlebitis of other and unspecified deep vessels of lower extremities Acute embolism and thrombosis of deep veins of lower extremity Pulmonary embolism	I80.1*; I80.2*; I82.3*; I26*	Sub-group of codes for exclusion of VTE in the restrictive definition within the clinical indication

* = wild card character indicating additional subcodes under this primary code; ICD-10-CM = International Statistical Classification of Diseases and Related Health Problems, 10th Revision, Clinical Modification, 2014 version. VTE = venous thromboembolism. Procedural codes will be included based on the dictionary system in place in each database.

** Primary prevention defined as prevention of the first VTE event after the index surgery:

Table 4 Preliminary list of diagnoses and corresponding ICD-10-CM codes to identify on-label and off-label use for stroke prevention in non-valvular atrial fibrillation with dabigatran etexilate

Disease/condition or procedure	ICD-10-CM description	ICD-10-CM code	Use of codes in indication definitions
Atrial fibrillation	Atrial fibrillation and flutter	I48*	Primary code for the broad definition of the clinical indication
Valvular heart disease	Non-rheumatic mitral valve, aortic valve, tricuspid valve, pulmonary valve disorders Endocarditis, valve unspecified Endocarditis and heart valve disorders in diseases classified elsewhere	I34*- I39*	Sub-group of exclusive codes for the restrictive definition within the clinical indication
	Chronic rheumatic heart diseases	I05*-I08*, I09.1	Sub-group of exclusive codes for the restrictive definition within the clinical indication
	Congenital malformations of pulmonary and tricuspid valves Congenital malformations of aortic and mitral valves	Q22*-Q23*	Sub-group of exclusive codes for the restrictive definition within the clinical indication
	Presence of heart valve replacement Presence of xenogenic heart valve	Z95.2* - Z95.4*	Sub-group of exclusive codes for the restrictive definition within the clinical indication

Table 4 (cont'd) Preliminary list of diagnoses and corresponding ICD-10-CM codes to identify on-label and off-label use for stroke prevention in non-valvular atrial fibrillation with dabigatran etexilate

Disease/condition or procedure	ICD-10-CM description	ICD-10-CM code	Use of codes in indication definitions
	Mechanical complication of heart valve prosthesis Mechanical complication of coronary artery bypass graft and biological heart valve graft Infection and inflammatory reaction due to cardiac valve prosthesis	T82.0* T82.2* T82.6*	Sub-group of exclusive codes for the restrictive definition within the clinical indication
Stroke, transient cerebral ischaemia (TIA)	Cerebral infarction; occlusion and stenosis of pre-cerebral or cerebral arteries; TIA; acute, but ill-defined, cerebrovascular disease; sequelae of cerebral infarction	I63*-I66* I69.3* G45	Secondary code to support clinical indication
Symptomatic heart failure	Heart failure	I50*	Secondary code to support clinical indication
Systemic embolism	Arterial embolism and thrombosis	I74*	Secondary code to support clinical indication
Diabetes	Diabetes mellitus	E10*-E11*	Secondary code to support clinical indication
Hypertension	Hypertensive disease	I10*-I15*	Secondary code to support clinical indication
Coronary heart disease	Ischaemic heart disease	I20*-I25*	Secondary code to support clinical indication

* = wild card character indicating additional subcodes under this primary code; ICD-10-CM = International Statistical Classification of Diseases and Related Health Problems, 10th Revision, Clinical Modification 2014 version. Procedural codes will be refined based on the dictionary system in place in each database

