3.1 POPULATION-BASED DATA SOURCES

The planned reimbursed launch of Pradaxa for the new (SPAF) indication has taken place sequentially across European countries. For this study, we are focusing on the United Kingdom (UK), reimbursement approved in August 2011; France, reimbursement approved in July 2012; and Denmark, reimbursement approved in August 2011. In all three countries, approved reimbursement for the SPAF indication is in place.

The use of dabigatran etexilate, in the approved indication for “primary prevention of venous thromboembolic events in adult patients who have undergone elective total hip replacement surgery or total knee replacement surgery” will be initiated and concentrated mainly in the hospital but could also extend to the outpatient setting for a limited period of time after hospital discharge. The standard dosing in the summary of product characteristics recommends starting treatment within 1 to 4 hours of surgery with a half dose of 110 mg and thereafter with 220 mg once daily (taken as two capsules of 110 mg) for 10 days after knee replacement and for 28 to 35 days after hip replacement [[R11-4002](#)].

For the approved SPAF indication, dabigatran etexilate is expected to be mainly prescribed, with some potential variations across European countries, by internal medicine specialists, cardiologists, and general practitioners (GPs), but most of the follow-up prescriptions (for chronic treatment) will be issued by GPs or primary care physicians. As the study implementation progresses through time, if new indications are approved for the use of dabigatran etexilate, new changes in the label will be taken into account for the characterisation of off-label use and contraindications.

This drug utilisation study, focused on describing the potential off-label use of dabigatran etexilate, will be conducted in automated health care databases in which information on prescriptions and disease occurrence (e.g., outpatient diagnoses, hospitalisations) is recorded

on an ongoing basis. Because most of the prescriptions of interest will be chronic and therefore expected to be captured in primary health care databases, the data sources will include the Clinical Practice Research Datalink (CPRD) in the UK, the French Cegedim Strategic Data (CSD) database, and the national databases in Denmark.

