3.3.5 Treatment indication

The indication or reason for treatment will be assessed according to the data available in the selected databases. The indication for a new course of treatment is most often not recorded in a systematic way in existing databases, and the degree of completeness of recording this information is variable across databases. In some primary health databases like the CPRD, the indication for a prescription is usually recorded the first time a new drug is prescribed by the general practitioner (GP). Similarly, the French Cegedim systematically records a clinical diagnosis associated with specific courses of medications. However, in the Danish national databases, data on indication is based on proxies.

It is expected that a proportion of new courses of dabigatran etexilate may not have a clearly associated clinical indication. Therefore, proxies for indication will be created using computer algorithms based on sets of diagnostic, procedural, and medication codes. These algorithms will be included in the detailed, database-specific study protocol. These indication-proxy algorithms will be helpful to search a time period before or concurrent with the index date. A minimum period of 1 year prior to the index date is considered the baseline period for determination of the clinical indication. However, all available historical data on diseases and medications might be used to develop valid algorithms for some indications.

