The proportion of users with each of the contraindications, including those based on comedication, disease, or severity of conditions, such as patients with severe renal impairment, will be also described. In those databases with laboratory test results available, severe renal impairment will be defined as creatinine clearance < 30 mL/min from directly recorded information of the estimated renal function, as available. For those patients with serum creatinine levels and patient weight available, we might estimate glomerular filtration rate by using the Cockcroft-Gault equation and/or the CKD-EPI equation [[R13-5416](#)]. However, it is important to be aware that actual values of laboratory test results will be inconsistently recorded in most databases and data will be limited. We will also capture those patients with ICD-10-CM codes for advanced renal disease—N18.4-N18.6, chronic kidney disease, stages 4 and 5 (severe), and end-stage renal disease—as available in each database according to the coding system and version in place.

Given the different recommended dosage regimens in both the approved and the new indications, new users of dabigatran etexilate will be described according to dose categories, but dose will not be included in the study definition of off-label use based on the first level of on-label indications.

Dose will be incorporated in the definition of off-label use based on the second level, which is a more restrictive definition of on-label use (see [Appendix 4](#)). In addition, the proportion of new users within the primary VTE prevention subgroup with one or more follow-up prescriptions after the recommended treatment duration will be described. The follow-up prescriptions will be assessed in the 90-day time window after the index prescription..

Table 5 Preliminary list of diagnoses and corresponding ICD-10-CM codes for identification of potential off-label clinical indications of dabigatran etexilate

Disease/condition or procedure	ICD-10-CM description	ICD-10-CM code	Use of codes in off-label indication definitions
Treatment or secondary prevention of venous thromboembolism	Venous thrombosis Pulmonary embolism	I80.1*, I80.2*, I82.3* I26*	
General thrombosis prophylaxis other than hip and knee orthopaedic surgery	Injuries to the knee and lower leg Fracture of femur	S80*-S89* S72*	In the absence of codes for hip or knee orthopaedic surgery (see Table 3)

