3.7 DATA ANALYSIS METHODS

The analyses will be descriptive at baseline. Assessment at baseline will include data for the 1 year before the index date, for the definition of the clinical indication, and all available data, for assessment of the prior history of diseases and conditions. All available data might also be used for medications included in the definition of certain proxies for indication. With these data, the following analyses will be performed in each database study:

- Age (including pediatric age) and sex distribution
- Proportion of patients with a prior diagnosis of specific diseases and conditions of interest listed in Sections [3.5](#) and [3.6](#)
- Proportion of patients with specific types of diseases as listed in Section [3.6](#)—prior to the index date
- Proportion of patients with renal function test performed during the baseline period and before the first prescription of dabigatran etexilate
- Proportion of patients using specific medications. Use of medications will be based on the 6 months prior to the index prescription.
- In the Cegedim (France) database, all the information from new users of dabigatran etexilate will be described by the type of panel and clinical specialty.

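### Table 3 qualifies hip/knee users as on-label through undated implant-presence codes, with no surgery-to-index interval and no criterion for elective surgery

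*Protocol*

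**What the plan says.** Protocol Section 3.5.1, Table 3, lists `Z96.64*` ("Presence of artificial hip joint") and `Z96.65*` ("Presence of artificial knee joint"). Each is marked "Primary code for the broad definition of the clinical indication". The restrictive level adds the absence of VTE codes between the operation and the start of dabigatran, and a footnote ties primary prevention to an index surgery. Section 3.5.2 brings dose into the restrictive level. The Table 3 note says that procedural codes will be included for each database.

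The indication quoted in Section 3.5.1 covers elective total hip or knee replacement. Section 3.1 gives the treatment length as "for 10 days after knee replacement and for 28 to 35 days after hip replacement".

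On look-back, Section 3.3.5 sets a minimum of 1 year and adds that "all available historical data on diseases and medications might be used to develop valid algorithms for some indications". Section 3.7 drops the word minimum: "Assessment at baseline will include data for the 1 year before the index date, for the definition of the clinical indication".

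In Table 5 (Section 3.5.2), knee or lower-leg injury and femur fracture are off-label only without a hip/knee code from Table 3. Malignancy and antiphospholipid syndrome are off-label only without a code from Table 3 or Table 4.

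Section 3.7.1 adds an analysis of long use: "The proportion of new users within the primary VTE prevention subgroup with one or more follow-up prescriptions after the recommended treatment duration will be described". A window of 90 days from the index prescription applies.

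**The concern.** A presence code is a lasting status, whereas the labelled use is a short course after a particular operation. With no limit on the interval, an old prosthesis is enough for the broad level. The restrictive level does not repair this: its VTE exclusion starts at a surgery date that a presence code does not give. Nor does either level separate elective replacement from replacement after a fracture. In Table 5 a hip/knee code removes the fracture class, so a non-elective replacement loses its off-label label.

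Two results are exposed. One is the off-label proportion, the main outcome, where the error runs towards too little off-label use. The other is the follow-up-prescription proportion. Its denominator is the VTE-prevention subgroup, which is likely to be small because Section 3.1 expects surgical use mainly in hospital and most captured prescriptions to be chronic. A few chronic AF users placed in that subgroup would change the result.

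**Working it through.** **The plan's own precision figure.** Exact (Clopper-Pearson) 95% intervals reproduce all 20 cells of Table 2. For 10% of 5,000 the interval is 9.18 to 10.87 (stated 9.2 to 10.9); for 5% it is 4.41 to 5.64 (stated 4.4 to 5.6). Table 2 is not in question and serves as a yardstick.

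**Look-back against treatment length.** The shortest look-back is 365 days. 365/35 = 10.4 times the longest cited course and 365/10 = 36.5 times the knee course.

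**Effect on the off-label proportion.** Let p be the true off-label proportion and q the share of off-label users with an old prosthesis, all of them moved to on-label. Then observed = p(1 − q), a relative loss of q. The protocol gives no value for q; 2% to 10% is assumed.

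| True p | q = 2% | q = 5% | q = 10% | Table 2 interval, n = 5,000 |
|---|---|---|---|---|
| 10% | 9.8% | 9.5% | 9.0% | 9.2 to 10.9 |
| 5% | 4.9% | 4.75% | 4.5% | 4.4 to 5.6 |

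Only the 9.0% falls outside its interval. AF users with a prosthesis do not alter this figure at the broad level, because their AF code already makes them on-label.

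**Effect on the follow-up-prescription proportion, if no rule puts AF first.** Let g be the share of new users who are genuine surgical users, with AF making up 90% of the rest and q now the prosthesis share among AF users. The AF share of the subgroup is c = 0.9(1 − g)q / [g + 0.9(1 − g)q]. Assume follow-up prescriptions after the recommended duration in 5% of surgical users and 80% of AF users; observed = 0.80c + 0.05(1 − c). All these inputs are assumptions.

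| g | c, q = 2% to 10% | Observed (true 5%) |
|---|---|---|
| 2% | 47% to 82% | 40% to 66% |
| 5% | 26% to 63% | 24% to 52% |
| 10% | 14% to 45% | 16% to 39% |
| 20% | 7% to 27% | 10% to 25% |

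For example, with g = 2% and q = 10%: 0.9 × 0.98 × 0.10 = 0.0882; c = 0.0882/0.1082 = 81.5%; observed = 0.80 × 0.815 + 0.05 × 0.185 = 66%.

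**The case against.** Much is deferred. Table 3 is called preliminary, procedural codes are to be added, the algorithms go to the database-specific protocols, and at least 200 profiles from the UK database (CPRD) will be reviewed to validate them. Codes are also not the only route: Section 3.3.5 says CPRD usually records an indication at first prescription and the French database records an associated diagnosis. These points reduce the likely effect. They do not remove it, because completeness varies, added codes neither displace the presence codes nor set an interval, and the profile review covers one database of three.

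Three stronger readings are tempting but not supported.

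- *Every user with an old prosthesis is on-label.* This holds at most at the broad level. At the restrictive level, VTE after surgery and dose can remove users. The Table 5 rows for VTE treatment and heart valve replacement have no exception for Table 3 codes, so a patient with deep vein thrombosis and an old prosthesis meets an on-label and an off-label rule. Section 3.5.2 does introduce its off-label list as applying where no labelled indication is present, but which rule wins for such a patient is not spelled out.
- *The follow-up-prescription analysis will consist mainly of AF patients.* That requires no AF-first rule. The text states no order of priority, but the Appendix 4 diagram, said to clarify the categories, was not in the text available for this review, so such a rule cannot be excluded.
- *Off-label use is overstated for long-standing AF because only 1 year is searched.* Section 3.3.5 and the synopsis treat 1 year as a minimum, and the synopsis says all available data will be used for components of certain proxies. The shorter statement in Section 3.7 is a wording conflict. If 1 year did bind, an old prosthesis would count only if coded again in that year.

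**Conclusion.** The point stands as a flaw in the definition. The common protocol lets an undated status code qualify a user, gives no interval or elective criterion at either level, uses a restrictive rule that those codes cannot support, and lets them cancel the off-label class for fracture or injury, malignancy and antiphospholipid syndrome.

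The bias in the main outcome is modest: a relative loss of 2% to 10% under the assumed prevalences, and less where the recorded indication or the Table 5 VTE and valve rows place users correctly. The bias in the follow-up-prescription proportion could be large, but only if AF users with a hip/knee code enter the VTE-prevention subgroup. The 10% to 66% range rests wholly on assumed prevalence, indication mix and refill rates.

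**What to change.** In the common protocol, so that all three databases follow the same rule before results are pooled:

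1. Require a dated hip or knee replacement procedure within a prespecified interval before the index date. Make it wide enough for first prescriptions that are captured late, since hospital starts can be missed; a limit as tight as the treatment course would drop possible overlong users.
2. Do not let a presence code alone qualify a user or override a Table 5 row. Where only such a code exists, report those users as a separate category, surgery date unknown, with a sensitivity analysis. This matters most in France, where Section 3.1.2 says there is no hospitalisation information.
3. State how elective surgery is identified in each database, or that it cannot be.
4. State which indication prevails when `I48*` and a hip/knee code coexist, and make Appendix 4 agree. Report the follow-up-prescription analysis with and without `I48*` patients; removing them outright would lose genuine surgical users who have AF.
5. Reconcile the 1-year wording in Section 3.7 with the minimum of 1 year and the use of all available data in the synopsis and Section 3.3.5.

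The cost is edits to Tables 3 and 5 and Sections 3.5 and 3.7, best made before the database-specific protocols are final. Some genuine surgical users without a dated procedure will move to the separate category, and its size should be shown.
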